
RESEARCH STRATEGY

Significance. SD in isolation or in combination with VT is a relatively rare disorder with a prevalence of 5.9 per 100,000 in the general population (Asgeirsson et al., 2006), although a significant portion of patients remains undiagnosed (Muller et al., 2002; Lo et al., 2009). SD develops spontaneously in midlife and progresses to become a chronic debilitating condition, which impacts nearly every aspect of a patient's life, causing emotional stress, loss of employment, social embarrassment and isolation. Thus, SD presents a significant, life-changing health problem for those who have it. In the course of their disorder, about 1/3 of SD patients develop action-induced VT, which additionally challenges their already impaired vocal communication. Clinically, the presence of VT in SD patients complicates the accuracy of diagnosis due to similarities between symptoms of these disorders, often leading to misdiagnosis and mistreatment, which are burdensome, both financially and psychologically. On the other hand, treatment of VT is not established. While SD symptoms can temporarily be managed with botulinum toxin injections, VT has a poor response to this treatment. No other pharmacological or surgical treatments have been specifically designed to provide long-term relief of symptoms of VT in SD patients. Based on a trial-and-error methodology, a minority of SD/VT patients receive such oral medications as propranolol, primidone, clonazepam and lorazepam, which, however, provide only mild benefits (Adler, 2000).

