1.1 Introduction. Although several lines of evidence suggest that abnormal brain function and structure in the key brain regions controlling sensorimotor aspects of speech production play an important role in the development of SD (Haslinger et al., 2005; Ali et al., 2006; [name] et al., 2008; [name] and Ludlow, 2010, 2011), the central mechanisms underlying the contribution of VT in SD are largely unknown. This gap in knowledge represents an important problem because it hinders the identification of improved treatment options for these patients. The objective of this aim is, therefore, to identify abnormalities of brain functional and structural organization in patients with SD vs. SD/VT. Supported by our strong preliminary data, our working hypothesis is that distinct brain abnormalities will be present in SD and SD/VT patients, who also share common abnormalities within the sensorimotor brain networks controlling voice production. We will test this hypothesis using the experimental approach of multi-modal neuroimaging, including functional MRI (fMRI), high-resolution MRI, and diffusion tensor imaging (DTI) to determine the organization of functional and structural speech-controlling networks, respectively, in SD vs. SD/VT vs. healthy controls. The rationale for these studies is that identification of VT-contributing brain changes in SD will allow us to develop neuroimaging biomarkers for the differential diagnosis of SD and SD/VT, as well as help identify treatment opportunities targeting specific brain abnormalities in these patients.

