Compared to controls, the patterns of regional abnormalities were *similar* in both SD and SD/VT patients. Decreased fractional anisotropy (FA), a marker of decreased white matter integrity and coherence, was found in the genu of the internal capsule, cerebral and cerebellar peduncles, and in the segment of the superior longitudinal fasciculus underlying the IFG and premotor cortex (**Fig. 2-I, upper left panel**, see next page). Commonly increased gray matter volume (GMV) in both SD and SD/VT patients, compared to controls, was observed in the primary laryngeal sensorimotor cortex, supramarginal gyrus, posterior cingulate cortex, ventral anterior thalamus, and cerebellum (**Fig. 2-II, lower left panel**).

Despite these similarities in brain structural abnormalities, SD and SD/VT patients exhibited somewhat *distinct* patterns of brain alterations. SD/VT showed *additional* FA decreases in the right premotor cortex and cerebellum (**Fig. 2-I, upper right panel**, *in green*) and GMV increases in the dorsal premotor cortex, ventral thalamus and cerebellar vermis (**Fig. 2-II, lower right panel**, *in green*). On the other hand, SD patients showed

additional FA decreases within the superior longitudinal fasciculus (**Fig. 2-I, upper right panel, in blue**) and GMV increases in the supramarginal and angular gyri (**Fig. 2-II, lower right panel, in blue**).

[figure not shown]

Figure 2 shows common (in yellow) and distinct (blue in SD and green in SD/VT) white matter (I) and gray matter (II) changes in SD and SD/VT patients ($p \leq 0.01$, corrected for multiple comparisons).

The results of our pilot neuroimaging studies, thus, strongly indicate the presence of both *shared and distinct* functional and structural alterations in SD and SD/VT patients, which can be found within the cortical and subcortical regions controlling sensorimotor aspects of voice and speech production. Compared to SD, SD/VT exhibits additional brain changes, which may potentially be targeted with novel treatment options. *Collectively, our data show that imaging techniques are capable of identifying differences in brain abnormalities between SD and SD/VT and support the feasibility of the below-proposed approach in our hands.*

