1.3.1 Study #1: Mapping disorder-specific brain activation in patients with SD vs. SD/VT using fMRI during symptomatic voice and speech production. We will use a sparse-sampling event-related BOLD fMRI design on a 3.0 Tesla Philips MRI scanner. We already successfully used this design for the investigations of voice and other laryngeal behaviors (Loucks et al., 2007; [name] et al., 2007; [name] et al., 2009; [name] and Ludlow, 2010). Brain activity will be studied during production of 10 symptomatic speech sentences (e.g., "We eat eels every day", "Sam has a rabbit in his hand") and syllables (repetitive vowel /i/ and continuous vowel /i/). In the scanner, subjects will listen to an auditory example of the task presented in a pseudorandomized order and reproduce it within the 5-s interval of the 'silent' period of scanning, only after which a 2-s image acquisition will follow, while the subjects remain silent and motionless. A resting condition without auditory presentation will serve as a baseline. Four scanning sessions will be acquired with a total of 36 experimental trials and 24 baseline conditions. Structural MRI will be acquired for an anatomical reference.

Data analysis will follow the similar processing pipeline as previously employed by us using AFNI software ([name] et al., 2007; [name] et al., 2009; [name] and Ludlow, 2010). Following initial data processing, the task-related responses will be analyzed using multiple linear regression with a single regressor for each task convolved with a canonical hemodynamic response function. Baseline drifts will be modeled using quadratic polynomials in time for each separate imaging run, and motion parameter estimates will be used as additional regressors of no interest in the multiple regression analysis. To account for disorder-specific vocal motor differences between SD and SD/VT groups, such as adductor and abductor voice breaks and shakiness, respectively, we will include the number of voice breaks and severity of voice tremor as variables in a within-group statistical analysis. Quantitative measures of SD and VT symptoms will be derived from the *Study 1.3.3* within this Aim. The correction of individual statistical parametric maps for multiple comparisons will be performed using Monte-Carlo simulations (Forman et al., 1995), which will identify a minimum cluster size at a voxelwise threshold of 0.005 at overall significance level of a corrected $p \leq 0.025$.

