The proposed studies, from univariate analysis to network modeling, are expected to provide full characterization of shared and distinct functional brain abnormalities between SD and SD/VT patients. This approach is feasible in our hand because we have already used similar analysis techniques in our previous studies ([name] et al., 2009; [name] and Ludlow, 2010, 2011).

Study population and Sample size. To estimate the number of subjects to be included in this study, we reviewed our recent fMRI study in SD patients, which used the similar fMRI experimental design ([name] and Ludlow, 2010). Significantly increased activation intensity was found in the primary somatosensory cortex during production of symptomatic syllables in SD patients compared to controls (mean % signal change \pm s.d.: SD vs. controls: 0.63 ± 0.16 vs. 0.39 ± 0.23 ; $p \leq 0.01$). Using these values, results of two-tailed t -test calculations suggest that a sample size of 15 subjects per group would have 80% power to detect group differences at a 0.025 significance level. The power for network analyses is the same. We propose to recruit 20 subjects per group to account for the subjects' dropout possibilities and to increase statistical power for detection of differences between groups.

1.3.2 Study #2: Mapping disorder-specific gray matter abnormalities in patients with SD vs. SD/VT using high-resolution MRI. In this study, we propose to identify GMV abnormalities that are common and distinct between SD and SD/VT patients. VBM is the most commonly used technique to identify changes in both cortical and subcortical gray matter in response to physiological and pathological conditions. To obtain VBM measures, we will acquire whole-brain high-resolution MR images (voxel size ≤ 1 mm isotropic) on a 3.0 Tesla Philips scanner within the same session of fMRI study described above.

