Data analysis. Similar to our recent study in SD ([name] and Ludlow, 2011), brain volume in each subject will be segmented into gray matter, white matter, and CSF. VBM analysis will follow the standard procedure using VBM8 toolbox in the SPM8 software. Spatial normalization will be performed using a diffeomorphic nonlinear registration tool (DARTEL) to improve inter-subject registration (Ashburner, 2007). Voxelwise statistical differences in GMV between groups will be examined using independent t -tests with age, gender, total intracranial volume, number of SD-specific voice breaks, severity of tremor and disorder duration as nuisance effects (Ashburner and Friston, 2000). The cluster-level significance will be assessed using a conservative non-stationary cluster extent correction (Hayasaka and Nichols, 2004) at $p \leq 0.025$.

Study population and Sample size. The same 3 groups of SD, SD/VT and healthy control subjects recruited for the fMRI study will participate in this study. To determine the sample size for this study, we reviewed our previous study in 40 SD patients and 40 controls ([name] and Ludlow, 2011). That study found increased GMV in the laryngeal primary sensorimotor cortex (HV vs. SD: 0.22 ± 0.04 vs. 0.26 ± 0.04). Using these values, t -test indicated that a sample size of 17 subjects per group will provide 80% power to detect group differ-

ences at a 0.025 significance level in the present study. To increase statistical power of the proposed studies and account for subjects' dropout possibilities, we will recruit the same 20 subjects per group, who participate in the 1.3.1. *Study #1*.

1.3.3 Study #3: Mapping disorder-specific white matter abnormalities in patients with SD vs. SD/VT using DTI.

In this study, we propose to identify white matter abnormalities contributing to SD and SD/VT using DTI on a 3.0 Tesla Philips scanner. Whole-brain brain images will be acquired using spin-echo EPI sequence with paired gradient pulses for diffusion weighting; diffusion will be measured along at least 33 non-collinear directions. We successfully used a similar scanning protocol in our previous studies ([name] et al., 2008; [name] et al., 2009).

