Data analysis. Blinded analysis of patients' voice samples will be performed to quantify the disorder severity, including the frequency of SD-specific voice breaks, voice harshness, breathiness, and voice tremor (see *Appendix 2*). In each patient group, unbiased whole-brain voxelwise Pearson's correlation coefficients will be computed to determine the relationships among brain activation (measured as percent BOLD signal change) and symptom severity at a corrected $p \leq 0.025$ using AFNI software ([name] and Ludlow, 2011). Similarly, whole-brain voxelwise Pearson's correlation coefficients will be used to assess relationships among measures of structural abnormalities (i.e., derived from VBM and DTI analyses) and quantitative measures of SD and VT symptoms (i.e., number of voice breaks, voice harshness, breathiness and voice tremor derived from voice and speech acoustic analysis). The alpha level will be set at $p \leq 0.025$ to correct for multiple comparisons.

1.4 Expected Outcomes. Upon the successful completion of the proposed studies in Specific Aim #1, it is our expectation that each disorder will have been found to exhibit a unique pattern of functional and structural al-

terations within the cortico-basal ganglia-thalamo-cortical and cerebello-thalamo-cortical networks. These findings will significantly advance our knowledge of SD and VT pathophysiology by establishing the concept that functional brain abnormalities in SD follow distinctive patterns when combined with VT. We expect that these findings will be fundamental in defining the neuroimaging markers of these disorders, which can be used for prediction and better differential diagnosis of SD and VT.

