All recruited subjects will be outpatient. To establish their eligibility for participation, *all* subjects will be first screened through the administration of the intake screening questionnaire, which will contain general questions about their health. SD patients will additionally be questioned about their disorder (e.g., onset, site, treatment, effects of alcohol of voice symptoms) (see **Appendix 1**).

Diagnosis of SD will be established based on the three-tiered approach as follows:

- (i) *the patients' self-screening questionnaire*, which will include questions regarding the amount of the effort required for speaking (e.g., Does it take a lot of work for you to talk?) and the presence of symptoms during different vocal activities (e.g., Can you do any of the following normally? Shout, Cry, Laugh, Whisper, Sing, Yawn) (**Appendix 2, Tier 1**);
- (ii) *voice and speech recording and evaluation*, which will include the acoustic analysis of 20 adductor sentences with a high number of glottal stops and vowels and 20 abductor sentences with a high number of voiceless consonants (/p/, /t/, /k/, /s/, /h/, /f/) produced in normal speaking voice and in a whisper (**Appendix 2, Tier 2**);
- (iii) *detailed laryngological examination*, which will include fiberoptic nasolaryngoscopy to observe the presence of vocal fold spasms during voice and speech production (**Appendix 2, Tier 3**);
- (iv) *detailed neurological examination*, which will be performed to exclude other neurological conditions, especially other forms of dystonia and tremor (**Appendix 2, Tier 3**).

Diagnosis of VT in SD will be established based on the following additional criteria:

- (i) Vocal tremor during vocalization that primarily involves laryngeal structures;
- (ii) Exclusion of other laryngeal pathologies based on fiberoptic nasolaryngoscopic examination.

We have successfully used this approach of subject selection in our previous studies. Furthermore, a recent pilot study of 30 patients with SD, VT and muscle tension dysphonia found 97% accuracy in the classification of these disorders using the above-described three-tiered approach.

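### The between-group VBM tests treat tremor severity, the feature that defines SD/VT, as a nuisance covariate; unless it is centred within group, the SD vs SD/VT contrast loses precision and part of its target

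*Combined protocol and SAP*

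**What the plan says.** The data analysis paragraph of section 1.3.2 (Study #2, VBM) compares GMV between groups by independent t-tests with six covariates: age, gender, total intracranial volume, and "number of SD-specific voice breaks, severity of tremor and disorder duration as nuisance effects". It does not say which covariates enter which contrast (patients vs controls, or SD vs SD/VT), and it does not say whether they are centred overall or within group.

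The purpose of the study is given in the same section: "we propose to identify GMV abnormalities that are common and distinct between SD and SD/VT patients". The rationale of Aim 1 (section 1.1) is that "identification of VT-contributing brain changes in SD will allow us to develop neuroimaging biomarkers for the differential diagnosis of SD and SD/VT". The pilot data (section 1.2.2, part II) reported, specific to SD/VT, "GMV increases in the dorsal premotor cortex, ventral thalamus and cerebellar vermis".

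Under Protection of Human Subjects, 1a, the added diagnostic criterion for VT in SD is "Vocal tremor during vocalization that primarily involves laryngeal structures", together with exclusion of other laryngeal pathology.

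The fMRI plan (section 1.3.1) handles the same variables differently: "we will include the number of voice breaks and severity of voice tremor as variables in a within-group statistical analysis". In section 1.3.4 (Study #4), Pearson "coefficients will be used to assess relationships among measures of structural abnormalities" and quantitative symptom measures, tremor among them.

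**The concern.** A nuisance covariate should be a source of variation that the comparison is not about. In SD vs SD/VT, tremor severity is close to a graded version of the group label: present in SD/VT by definition and expected to be near zero in SD. Two things follow if it is entered without within-group centring.

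- **Precision.** The group coefficient becomes the difference at equal tremor. Few or no patients supply that comparison, so its standard error grows.
- **Target.** Any part of the GMV difference that varies with tremor is credited to the covariate. That is the part most closely tied to VT, which the aim sets out to find.

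A null result would then be hard to read: the groups may not differ, or the difference may have been adjusted away.

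Voice breaks and disorder duration are not the problem in this contrast. Both are defined in both patient groups, and duration is a plausible confounder because VT appears over time (Significance: "In the course of their disorder, about 1/3 of SD patients develop action-induced VT").

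The patient vs control tests raise a point to clarify. Read literally, the sentence also enters duration, which is undefined in controls, and symptom scores, which are about zero there.

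**Working it through.** **1. The plan's own figure.** Section 1.3.2 gives GMV of 0.22 ± 0.04 (controls) and 0.26 ± 0.04 (SD), so d = 0.04/0.04 = 1. It states 17 per group for 80% power at 0.025. For an unadjusted two-sample t-test the noncentrality is d·√(n/2) on 2n − 2 degrees of freedom.

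- n = 17: √8.5 = 2.92 on 32 df. Power is 80.7% at one-sided 0.025 and 71.2% at two-sided 0.025.
- n = 20: √10 = 3.16 on 38 df. Power is 86.9% and 79.3%.

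The 17 therefore reproduces at one-sided 0.025 (equivalently two-sided 0.05), for controls vs SD and without covariates. It does not describe the six-covariate model, and no power is stated for SD vs SD/VT.

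**2. Assumptions.** The documents give neither a tremor distribution nor an SD vs SD/VT effect size. I borrow d = 1, take 20 per group, and treat one test without cluster correction. Tremor is zero in SD; in SD/VT its mean/s.d. ratio is k = 0.5 to 4.

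**3. Variance inflation.** With equal groups, the between-group variance of tremor is m²/4 and the average within-group variance is s²/2. With k = m/s:

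r² = (m²/4)/(m²/4 + s²/2) = k²/(k² + 2), and VIF = 1/(1 − r²) = 1 + k²/2.

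At k = 1, VIF = 1.5; at k = 2, VIF = 3, so the standard error grows by √3 = 1.73. Dividing the noncentrality by √VIF, with six covariates, gives power at 20 per group of 71% (k = 1) and 42% (k = 2) one-sided, or 59% and 31% two-sided. Without tremor (five covariates) it is 87% and 79%.

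**4. Simulation.** This adds what the formula leaves out: chance imbalance of every covariate and skewed (gamma) tremor scores. It used 6,000 replicates, with gender 16:4 in each group and covariates other than tremor independent of group. Variance is relative to the unadjusted t-test.

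| Model | Tremor–group correlation | Variance | Power, one-sided 0.025 | Power, two-sided 0.025 |
|---|---|---|---|---|
| Age, gender, ICV | – | 1.06 | 85% | 77% |
| + breaks, duration | – | 1.12 | 82% | 73% |
| + tremor, k = 0.5 | 0.39 | 1.35 | 76% | 65% |
| + tremor, k = 1 | 0.61 | 1.87 | 62% | 50% |
| + tremor, k = 2 | 0.83 | 3.93 | 37% | 26% |
| + tremor, k = 3 | 0.91 | 7.34 | 22% | 14% |
| + tremor, k = 4 | 0.95 | 12.16 | 15% | 9% |

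One-sided sensitivity:

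- If SD patients have a quarter of the SD/VT tremor, the five tremor rows become 80%, 72%, 50%, 33% and 23%.
- At k = 2, adding tremor takes power from 64% to 26% for d = 0.8, and from 93% to 48% for d = 1.2.
- If tremor is centred within group, power stays at 82–83%.

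**5. Shift of target (k = 2, total difference 1 s.d., one-sided 0.025).**

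| Share of difference tracking tremor | Mean adjusted estimate | Power with tremor | Power without tremor |
|---|---|---|---|
| 25% | 0.75 | 22% | 82% |
| 50% | 0.51 | 13% | 82% |
| 75% | 0.26 | 6% | 80% |
| 100% | 0.00 | 2.5% | 79% |

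**6. Can the within-group correlation replace the contrast?** Power of the tremor correlation in 20 SD/VT patients, against the group model without tremor, both at two-sided 0.025:

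| Ratio and share tracking tremor | Within-group correlation | Group model without tremor |
|---|---|---|
| k = 2, half | 11% | 73% |
| k = 2, all | 41% | 69% |
| k = 1, half | 39% | 68% |
| k = 1, all | 87% | 55% |

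It replaces the contrast only in part. It does better when tremor varies widely and drives the whole difference.

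**7. Patients vs controls, only under the literal reading** (breaks and duration coded zero in controls; 3,000 replicates). One-sided power falls from 85% to 50%, 24%, 14% and 11% at ratios 1 to 4. If breaks and duration correlate at 0.6, it falls to 59%, 31%, 18% and 13%.

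**The case against.** The best defence is that the adjusted contrast answers a legitimate question: do the groups differ in GMV beyond what symptom severity explains? Structure that follows severity has its own analysis in section 1.3.4, and the fMRI plan shows that the sponsor thought about severity. That question can stand as a secondary one. It is not the stated target, and the fMRI plan confines these variables to within-group analysis, which the VBM text does not.

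Second, within-group centring would remove the power loss. That is correct, but section 1.3.2 does not specify it, so the text needs correcting in either case.

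Third, the size is assumed. This stands. The effect size is borrowed from controls vs SD, near-zero tremor in SD is an inference from the diagnostic criteria, and at ratio 0.5 the loss is small (82% to 76%). The direction follows from how the groups are defined; the magnitude does not.

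Fourth, the 82% benchmark is a best case because duration is simulated as independent of group. If duration differs by 1 s.d. between the groups, the model without tremor falls from about 83% to 73% one-sided. That is the price of adjusting for a plausible confounder and does not argue for adding tremor.

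Fifth, the reach is limited. The fMRI and DTI plans state no tremor covariate for their between-group comparisons, so the point concerns VBM only. The patient vs control figures depend on a reading that the sponsor may not intend, and they do not carry the conclusion.

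**Conclusion.** The concern holds and should be settled before analysis. As written, the VBM model adjusts the SD vs SD/VT contrast for the feature that defines one of the two groups, and no other section supplies an SD vs SD/VT GMV contrast free of tremor.

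Under the illustrative assumptions, power at one-sided 0.025 drops from 82% to between 76% and 15%. The loss is modest at a tremor mean/s.d. ratio of 0.5 and large from ratio 2. The shift of target arises only where GMV varies with tremor; if it does not, precision alone is lost. Both effects disappear if tremor is centred within group. Confidence is high on direction and on the conflict with the stated aim; the size cannot be fixed from the documents.

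**What to change.** Replace the covariate sentence in section 1.3.2 with text along these lines:

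> Patient vs control contrasts will be adjusted for age, gender and total intracranial volume. The SD vs SD/VT contrast will be adjusted for age, gender, total intracranial volume, number of voice breaks and disorder duration; tremor severity will not be entered. Tremor severity, voice breaks and disorder duration will be related to GMV within patient groups (Study 1.3.4). A between-group model that also includes tremor severity is a sensitivity analysis, with centring stated in advance.

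Two details to settle with it. The tremor correlation will be informative mainly in SD/VT, since tremor is expected to be near zero in SD. Disorder duration is a small addition to Study 1.3.4, which now names only voice and tremor measures.

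The cost is a few sentences of analysis text, with no new data and no change in sample size. The downside is that the primary group differences are not adjusted for tremor severity, and the patient vs control differences are not adjusted for any symptom measure.

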For group analysis, the 3-D anatomical datasets of each subject will be spatially normalized and converted to the standard anatomical space. The resulting normalization parameters will be applied to the 4-D time series datasets. To estimate the main effect of a task per group, the group analysis will be carried out using a three-way analysis of variance (ANOVA) with subject as a random factor and the task and group as fixed factors ($p \leq 0.025$, voxelwise corrected) to identify (1) shared abnormalities in all patients vs. controls, and (2) distinct abnormalities between SD vs. SD/VT patients. Statistical differences in brain activation extent will be assessed using the subtraction method within the three-way ANOVA design. This univariate data analysis will provide information about the extent and intensity of brain activation in different groups (i.e., SD and SD/VT patients vs. controls and SD patients vs. SD/VT patients).

To further our knowledge of functional brain abnormalities in SD and VT, we will perform multi-stage brain network analysis, which will allow for identification of abnormal brain networks and the relationship between the key network regions, possibly contributing to the pathophysiology of these disorders. For this, we will first perform a correlation analysis between functional and structural datasets in SD and SD/VT patients to determine the brain regions of abnormal function with underlying structural changes. The structural data will be derived from the *Studies 1.3.2 and 1.3.3*.

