Study population and Sample size. To estimate the number of subjects in this study, we reviewed our recent DTI studies, which used a similar experimental design to examine white matter abnormalities in SD patients and controls ([name] et al., 2008; [name] et al., 2009). Significantly decreased FA was found in the right genu of the internal capsule in SD (patients vs. controls: 0.55 ± 0.05 vs. 0.61 ± 0.07). Using these values, a power of 80% at a 0.025 significance level will be obtained with 18 subjects per group for the proposed study based. Again, to increase the statistical significance and allow for between-study comparisons, we propose to recruit the same 20 subjects per SD, SD/VT and control group for the DTI study. The statistical power for tractography is the same.

1.3.4 Study #4: Relationship between brain abnormalities and clinico-behavioral characteristics in SD and SD/VT.

The role of neuroimaging studies in elucidation of pathophysiological mechanisms of SD would be considerably enhanced if coupled with strategies that yield information about their relevance to symptom elicitation. Additionally, identification of disorder-specific brain abnormalities that are correlated with disorder symptoms can prove useful for assessment of efficacy of existing and newly developed therapeutic interventions. Our approach here will be to examine the relationships of functional brain activity and structural brain organization with clinico-behavioral correlates (i.e., disorder severity scores). For all 20 subjects per group (both patients and controls), the behavioral measures will be obtained during initial intake screening, history and physical examination, and three-tiered diagnostic questionnaire (see *Appendices 1 and 2*). Patients' voice and speech will be digitally recorded during scanning for offline acoustic analysis to assess the SD and VT severity.

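### One 0.025 label covers two error-rate conventions: from the printed inputs, fMRI n = 15 fits only two-tailed 0.025, while VBM n = 17 and DTI n = 18 fit only one-sided 0.025

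*Combined protocol and SAP*

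**What the plan says.** All three calculations are in section 1.3 (Research Design, Specific Aim #1), under the Study population and Sample size paragraphs.

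- **1.3.1, fMRI.** The inputs are percent signal change, "SD vs. controls: 0.63 ± 0.16 vs. 0.39 ± 0.23". The sidedness is given: "results of two-tailed t -test calculations suggest that a sample size of 15 subjects per group" reach 80% power at 0.025.
- **1.3.2, VBM.** The inputs are grey matter volume 0.22 ± 0.04 in controls and 0.26 ± 0.04 in SD. A t-test "indicated that a sample size of 17 subjects per group will provide 80% power to detect group" differences, again at 0.025. No sidedness is given. On recruitment, to increase power and to cover "dropout possibilities, we will recruit the same 20 subjects per group".
- **1.3.3, DTI.** The inputs are fractional anisotropy 0.55 ± 0.05 in patients and 0.61 ± 0.07 in controls. The result is "a power of 80% at a 0.025 significance level will be obtained with 18 subjects per group for the proposed study". Neither test nor sidedness is named. The same 20 per group are used; this paragraph makes no dropout claim.

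Each paragraph presents its result as calculated from the values it prints, and none says that the convention changes. All three effects are SD patients against controls. The group analysis in 1.3.1 also tests for "distinct abnormalities between SD vs. SD/VT patients".

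**The concern.** The VBM and DTI effects (about 1.0 SD) are clearly smaller than the fMRI effect (about 1.2 SD), yet the stated sizes rise only from 15 to 17 and 18. With power and significance level fixed, n per group is roughly proportional to 1/d². Moving from d = 1.211 to d = 1.000 should raise n by a factor of about (1.211/1.000)² = 1.47, so 15 should become about 22, not 17. That suggests the 0.025 does not mean the same thing in each study.

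A reader therefore cannot tell which type I error rate the two structural studies were sized on. If it is the two-tailed rate stated for fMRI, 17 and 18 do not deliver 80% power, and the step from 17 to 20 for VBM is not the reserve it is said to be.

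**Working it through.** **Method.** Two-sample t-test with equal groups of n. Standardised effect d = |difference in means| / √((s₁² + s₂²)/2). Power comes from the noncentral t distribution with 2n − 2 degrees of freedom and noncentrality d√(n/2). The critical value is the 1 − 0.0125 quantile for two-tailed 0.025, and the 1 − 0.025 quantile for one-sided 0.025. One-sided 0.025 gives the same sizes as two-sided 0.05.

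**Effects from the printed inputs.**

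- fMRI: 0.24 / √((0.16² + 0.23²)/2) = 0.24 / 0.198 = 1.211
- VBM: 0.04 / 0.04 = 1.000
- DTI: 0.06 / √((0.05² + 0.07²)/2) = 0.06 / 0.0608 = 0.986

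**Reproducing the stated sizes** (smallest n with at least 80% power):

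| Study | Stated n | Two-tailed 0.025 | One-sided 0.025 |
|---|---|---|---|
| fMRI | 15 | **15** (82.3%; 14 gives 79.0%) | 12 |
| VBM | 17 | 21 (81.5%) | **17** (80.7%; 16 gives 78.1%) |
| DTI | 18 | 21 (80.3%) | **18** (82.0%; 17 gives 79.6%) |

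Each stated figure is exactly the smallest adequate n under one convention and not under the other. The Welch test gives the same sizes. The normal approximation gives 13/20/20 two-tailed and 11/16/17 one-sided, so it does not give 15/17/18 either. Using only the larger SD moves one-sided fMRI to 15 (normal) or 16 (t), but it moves one-sided DTI to 22 or 23, so it does not restore a single convention.

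**Power if two-tailed 0.025 applies throughout.** The plan gives no dropout rate; 19 and 18 completers are illustrations.

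| n per group | VBM | DTI |
|---|---|---|
| 17 (stated, VBM) | 71.2% | – |
| 18 (stated, DTI; or 2 lost per group from 20) | 74.1% | 72.8% |
| 19 (1 lost per group from 20) | 76.8% | 75.6% |
| 20 (planned) | 79.3% | 78.1% |
| 21 | 81.5% | 80.3% |

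The normal approximation puts power at 20 at 82.1% and 81.0%. fMRI at 20 has 92.8% by the exact test.

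**Power if one-sided 0.025 is meant for VBM and DTI.** At 20 per group it is 86.9% and 86.0%. VBM could then lose three per group and still have 80.7%.

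**Rounding.** Each printed mean and SD can be off by up to 0.005. At the extremes:

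- fMRI: d from 1.13 to 1.29; n from 13 to 17 two-tailed and 11 to 14 one-sided. On the pooled SD, 15 therefore cannot be a one-sided result.
- VBM: d from 0.67 to 1.43; n from 11 to 45 two-tailed.
- DTI: d from 0.76 to 1.25; n from 14 to 35 two-tailed.

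For two-tailed 0.025 to give 17 and 18, the unrounded effects would have to be at least 1.10 SD (VBM) and 1.07 SD (DTI). Both lie inside the rounding ranges.

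**The case against.** The best counter-argument is rounding. A VBM difference of 0.043 with SD 0.039 prints as 0.04 and 0.04 and gives 17 at two-tailed 0.025. DTI means of 0.5475 and 0.6125 print as 0.55 and 0.61 and give 18. One convention could then lie behind all three sizes, with the true inputs in source studies that are not available here. This stands as a possibility, so the finding is limited to the printed inputs. It does not remove the fault: each paragraph says its result was calculated from the values shown, and those values do not give it.

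Second, the VBM and DTI paragraphs never say two-tailed, and a one-sided 0.025 is compatible with their wording. That is also right. The loss of power and of the dropout reserve follows only if the fMRI convention is carried over. On the one-sided reading VBM has a real margin at 20.

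Third, the practical effect is small. Every Aim 1 study recruits 20 per group, and the least favourable reading costs 1 to 2 points at that size. The planned analyses are voxelwise and corrected, so a single-region t-test is a rough guide anyway. This limits the weight of the point but does not make the figures correct.

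Fourth, pooling all patients against controls would raise power. Assuming 40 versus 20 and the same effect in SD/VT, two-tailed power is about 91% (VBM) and 90% (DTI). However, the plan states its sizes per group, and the pooled contrast is not the one it sized.

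Last, the missing power for SD versus SD/VT is a separate matter from sidedness. It is noted here as a clarification, and the conclusion does not depend on it.

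**Conclusion.** The point holds. From the printed inputs, no single meaning of a 0.025 significance level yields 15, 17 and 18 per group: two-tailed gives 15/21/21 and one-sided gives 12/17/18.

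If two-tailed 0.025 is meant throughout, power at the stated sizes is about 9 points (VBM) and 7 points (DTI) below 80%. At the planned 20 it is at most 2 points below before any dropout, and VBM has no reserve. If one-sided 0.025 is meant for VBM and DTI, their figures are right, but the convention differs from that of fMRI without the plan saying so.

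These results assume equal groups, the exact t-test with pooled SD, and the inputs as printed. The consequence is inconsistent figures and, on the two-tailed reading, an unsupported dropout statement for VBM; the study is not seriously undersized for the contrasts it was sized on. The stated 80% covers SD versus controls only. It says nothing about SD versus SD/VT.

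**What to change.** State one sidedness for all three calculations in 1.3.1 to 1.3.3, and print the unrounded inputs if those were used. Then:

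- **If two-tailed 0.025 with the printed inputs:** replace 17 and 18 with 21, restate power at the planned 20 as about 79% (VBM) and 78% (DTI), and delete the statement in 1.3.2 that 20 allows for dropout.
- **If one-sided 0.025 for VBM and DTI:** say so, and either align the fMRI calculation (12 per group) or explain why it differs.
- **In either case:** state that the three calculations concern SD versus controls and not SD versus SD/VT. If a detectable SD versus SD/VT difference is quoted (about 1.0 SD at 20 per group, 80% power, two-sided 0.025), label it as applying to a single uncorrected t-test, not to the planned voxelwise, corrected and covariate-adjusted analyses.

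The cost is wording and restated figures. Recruitment stays at 20 per group; on the two-tailed reading the quoted power is slightly less favourable.
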